12.1.3.1 Eligibility Checklist

The Eligibility Checklist must be completed by the Research Nurse and CRA and signed by an authorized investigator prior to registering the subject. See Section 4.3 for the registration procedure.

12.2 Protocol Deviations

12.2.1 Deviation Policy

This protocol will be conducted in accordance with COH's "Clinical Research Protocol Deviation Policy" located at

<http://www.coh.org/dsmc/Documents/Institutional%20Deviation%20Policy.pdf>.

Deviations from the written protocol that could increase patient risk or alter protocol integrity require prior IRB approval of a single subject exception (SSE) request. In addition, if contractually obligated, the sponsor must also approve the deviation. IRB pre-approved SSE protocol modifications are considered an amendment to the protocol and not a deviation. The submission of a deviation report is not required.

Brief interruptions and delays may occasionally be required due to travel delays, airport closure, inclement weather, family responsibilities, security alerts, government holidays, etc. This can also extend to complications of disease or unrelated medical illnesses not related to disease progression. The PI has the discretion to deviate from the protocol when necessary so long as such deviation does not threaten patient safety or protocol scientific integrity. Examples include, but are not limited to: a) dose adjustments based on excessive patient weight; b) alteration in treatment schedule due to non-availability of the research participant for treatment; c) laboratory test results which are slightly outside the protocol requirements but at levels that do not affect participant safety. These instances are considered to be deviations from the protocol. A deviation report will be submitted to the DSMC/IRB within five days.

12.2.2 Reporting of Deviations

All deviations will be reported to the COH DSMC within five days. The DSMC will forward to report to the IRB following review.

12.2.3 Resolving Disputes

In situations where there is misperception or dispute regarding a protocol deviation among the persons involved in implementing the protocol, it is the responsibility of the PI to resolve the dispute and the PI may consult with the DSMC chair (or designee) to arrive at resolution.

13.0 Statistical Considerations

13.1 Study Design

13.1.1 Sample Size Calculation and Power Analysis

We will need 128 patients (64 per arm) to detect an effect size of 0.5 in the primary outcomes as described in Aim 2 (postoperative complications, lower readmission rates, improved symptoms, QOL, and functional recovery) between the two groups, with a two-sided 0.05 significance level using a two-sample t-test and at least 80% power. We will enroll a total of 160 (80 per arm to account for an expectation of 20% attrition. Thus, we will have sufficient power for all primary outcomes, including our primary endpoint of postoperative complications.

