13.2.1.2 Statistical Methods by Study Aims

We are proposing a two-group, randomized control design in which participants recruited into the study will be randomly assigned into the enhanced usual care (control) arm or the telemonitoring (intervention) arm. Both groups will be followed over the same time period which includes preoperative measurements and then up to 30 days post discharge. Data will be collected at five time points (T1: baseline, T2: pre-discharge, T3: 7-day post-discharge, T4: 14-day post-discharge, T5: 30-day post discharge). The primary outcomes for hypothesis testing are found in Aims 2, including postoperative complications, lower readmission rates, improved symptoms, QOL, and functional recovery. The primary endpoint is severity (grade) of postoperative complications from discharge to day 30 post-discharge. Descriptive statistics will be used to summarize all variables. For continuous variables, we will provide mean \pm standard deviation (SD), median, range, and sample size. For categorical variables, we will include sample size and proportion.

Specific Aim 1: Assess the feasibility, retention, and acceptability of the remote perioperative telemonitoring intervention as measured by the percentage of patients who a) agree to participate; b) complete $\geq 70\%$ of the telemonitoring; and c) report satisfaction with the intervention through structured exit interviews.

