Feasibility will be assessed through: 1) the ratio of eligible participants to those enrolled and those who declines participation; 2) reasons for non-participation; 3) number of scheduled study encounters completed; 3) attrition rate between pre- and post-discharge; 4) reasons for attrition/dropout; 5) the ratio of all participants to those who completed $\geq 70\%$ of the study; These data will be descriptively reported and analyzed. Qualitative data on acceptability from exit interviews will be analyzed using the conventional content analysis approach.⁶⁵ This approach is used to describe a phenomenon where existing theory or research literature is limited. Data from the audio-recorded interviews will be transcribed and analyzed using HyperRESEARCH™ qualitative software. Transcripts will be imported allowing for the development of analytic categories, data coding, and review of coded data. All data will be read repeatedly to achieve immersion and obtain a sense of the whole. Then, data will be read word by word to derive codes. Codes will then be sorted into themes based on links and relationship. Separate investigators ([name] and [name]) will conduct a final validation review of the codes and themes to ensure consistency and clarity across all qualitative data. Data discordantly coded will be discussed for refinement and consensus purposes.

Specific Aim 2: Determine the preliminary efficacy of the remote perioperative telemonitoring intervention on surgical outcomes, healthcare utilization, PROs, and functional recovery.

Hypothesis 2.1: Patients randomized to the telemonitoring arm will experience reduced severity (grade) of postoperative complications, lower readmission rates, and improved symptoms, QOL, and daily steps.

For Specific Aim 2, the primary endpoint is the change in Comprehensive Complications index (CCI) from discharge to day 30 post-discharge. First, change in CCI will be computed. A two-sample t-test will be conducted to determine if there is significant difference between mean CCI of the intervention arm and the control arm. Trends in CCI scores will be explored over time (T2-T5). Exploratory within subjects' correlation will be examined using Pearson correlation between adjacent time points. A random-effects model will be used to study group differences in mean over time. Other variables (e.g., age and sex) may be included in the model to adjust for possible confounding.

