Similar analysis will be carried out for repeatedly measured secondary endpoints (symptom severity score, QOL). Generally speaking, we expect better scores in the intervention arm than the control arm. Healthcare resource use (e.g., hospital readmission) is a secondary endpoint. At each time point, we will estimate the ER visits/readmission rates and provide confidence intervals for each arm. Further, a binomial test for comparing two proportions will be conducted to see if there is significant difference between the readmission rates of the two arms. For simplicity, Bonferroni correction will be used both in the proportions comparisons test and the confidence intervals construction.

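### The claim of sufficient power for all primary outcomes fails for readmission, whose planned Bonferroni-corrected test has about 66% power with three comparisons at 64 per arm

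*Combined protocol and SAP*

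**What the plan says.** Section 13.1.1, repeated in the synopsis under Statistical Considerations, asks for 128 evaluable patients (64 per arm). The basis is effect size 0.5, two-sided 0.05, a two-sample t-test and at least 80% power. Allowing for 20% attrition gives 160 enrolled. Five outcomes are named as covered: complications, readmission, symptoms, QOL and functional recovery. The section ends: "Thus, we will have sufficient power for all primary outcomes, including our primary endpoint of postoperative complications".

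Section 13.2.1.2 repeats the list: "The primary outcomes for hypothesis testing are found in Aims 2, including postoperative complications, lower readmission rates, improved symptoms, QOL, and functional recovery". It then gives a single primary endpoint: "For Specific Aim 2, the primary endpoint is the change in Comprehensive Complications index (CCI) from discharge to day 30 post-discharge".

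Further on, the same section treats the other outcomes differently:
- Readmission: "Healthcare resource use (e.g., hospital readmission) is a secondary endpoint".
- Symptoms and QOL: "Similar analysis will be carried out for repeatedly measured secondary endpoints (symptom severity score, QOL").
- Readmission test: "a binomial test for comparing two proportions will be conducted to see if there is significant difference between the readmission rates" of the two arms.
- Multiplicity: "For simplicity, Bonferroni correction will be used both in the proportions comparisons test and the confidence intervals construction".

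No divisor, control readmission rate or target difference in rates is given anywhere.

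**The concern.** The stated power belongs to one test at one alpha (t-test, 0.05). The readmission analysis is another test at a smaller alpha of unknown size. Bonferroni only makes sense with more than one comparison, so the alpha for readmission must be 0.025 or less, and 64 per arm was chosen to just reach 80% at 0.05.

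The status of the outcomes also conflicts. Readmission, symptoms and QOL are primary in the synopsis, in 13.1.1 and early in 13.2.1.2, but secondary at the end of 13.2.1.2. Functional recovery is on the primary list, yet 13.2.1.2 gives it no separate label and no named test.

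Section 1.0 says the findings will shape a Phase III trial. A null readmission result could be carried into that planning as adequately powered when it was not.

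**Working it through.** **Inputs.** From 13.1.1: effect size 0.5, two-sided alpha 0.05, 64 evaluable and 80 enrolled per arm. From 13.2.1.2: two-proportion test, Bonferroni, divisor m not stated.

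**1. The plan's own figure.** For a two-sample t-test with n per arm, the noncentrality is d√(n/2) = 0.5 × √32 = 2.828 on 126 degrees of freedom. The critical value at two-sided 0.05 is 1.979, and power is 80.1%. The smallest n reaching 80% is 64. Enrolment is 128 / 0.8 = 160. Both stated figures reproduce.

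**2. What m could be.**
- The SAP's post-discharge visits are "T3: 7-day post-discharge, T4: 14-day post-discharge, T5: 30-day post discharge", which gives three.
- Table 1 (section 11.1) has three readmission marks, read as days 7, 14 and 30.
- The Study Calendar (section 10.0) has four, adding day 2.
- Section 13.2.1.2 estimates rates at every time point, pairs ER visits with readmission, and then names one test.
- Section 12.1.3 has the chart audit capture readmissions at 30, 60 and 90 days.

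Three fits the SAP best, but it is an inference.

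**3. The same t-test at alpha 0.05/m, d = 0.5.**

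| m | alpha | Power, 64 per arm | Power, 80 per arm | n per arm for 80% |
|---|---|---|---|---|
| 1 | 0.0500 | 80.1% | 88.2% | 64 |
| 2 | 0.0250 | 71.2% | 81.5% | 78 |
| 3 | 0.0167 | 65.6% | 77.0% | 86 |
| 4 | 0.0125 | 61.6% | 73.7% | 91 |

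For m = 3 at 64 per arm, the noncentrality stays at 2.828 and the critical value rises to 2.426.

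**4. The test actually planned.** For a proportion, read effect size 0.5 as Cohen's h = 2·arcsin√p1 − 2·arcsin√p2. The control rate is assumed to be p1 = 1/3. The nearest figure in the documents, in section 1.0, is about one third, but it describes patients who become symptomatic from a complication and may need readmission, so it is not a readmission rate. Then p2 = sin²(arcsin√(1/3) − 0.25) = sin²(0.6155 − 0.25) = 0.128. Power of the pooled z test, summed over all pairs of binomial outcomes:

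| m | 64 per arm | 80 per arm |
|---|---|---|
| 1 | 80.4% | 88.7% |
| 2 | 71.7% | 81.9% |
| 3 | 65.9% | 77.0% |
| 4 | 62.5% | 73.7% |

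With h = 0.5 held fixed and assumed control rates from 20% to 50%:

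| m | 64 per arm | 80 per arm |
|---|---|---|
| 2 | 70–72% | 80–83% |
| 3 | 65–67% | 76–78% |
| 4 | 59–63% | 73–74% |

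A lower control rate makes it worse: at 10%, three comparisons with 64 per arm give 52.8%.

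**5. What h = 0.5 demands.** It is a fall from 33% to 12.8%. If the rate were halved instead (33.3% to 16.7%, an illustration), power at 64 per arm by the pooled normal formula would be 58.8% unadjusted and 41.3% with m = 3.

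**The case against.** The strongest reply is that 66% is conditional. It needs a divisor of three, effect size 0.5 read as h, and 64 evaluable per arm, and the plan states neither of the first two. Readmission comes from chart audit, so missing device or questionnaire data need not remove a patient. With all 80 per arm evaluable, two comparisons reach 81–82% in the calculations above and three miss by only about three points. Much of this stands: the supportable general statement is that the divisor is undefined and that any value of two or more misses 80% at the planned 64. It does not rescue the claim, because three or four comparisons fail at 80 per arm as well.

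It can also be said that no shortfall is shown for symptoms or QOL. That is right. They follow the t-test approach, and Bonferroni is attached only to the proportions test and the intervals, so each keeps 80.1% at d = 0.5. For them the defect is the label, not the power. A single unadjusted day-30 readmission test would likewise restore about 80% at h = 0.5, but that is not what 13.2.1.2 describes.

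Finally, this is a pilot seeking preliminary efficacy, and the primary test is sound. That limits the weight of the point, but the plan itself chose to claim power for readmission.

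**Conclusion.** The point holds and should be fixed. The sample size, enrolment and CCI test are correct. The extension of 80% power to readmission is not supported by the analysis planned for it:
- At 64 evaluable per arm, every divisor of two or more falls below 80%, with about 66% for three and 62% for four.
- At 80 per arm, three give about 77% and four about 74%. Two pass for control rates of 20–50%.

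All of this rests on effect size 0.5 carrying over to proportions as h = 0.5; the two-proportion figures also rest on an assumed control rate. The count of three is inferred. The missing divisor and the primary/secondary conflict need no assumption: they can be read directly from the text.

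**What to change.** 1. In the synopsis and 13.1.1, limit the 80% power statement to the CCI endpoint and drop the claim for all primary outcomes.
2. Remove the five-item primary list from the synopsis, 13.1.1 and 13.2.1.2. Label the other four outcomes secondary throughout, as the end of 13.2.1.2 already does for readmission, symptoms and QOL, and name a test for functional recovery.
3. State the Bonferroni divisor for readmission, and whether ER visits count towards it. Reconcile the readmission time points in the Study Calendar, Table 1 and 13.2.1.2, and say how the 30-, 60- and 90-day windows in 12.1.3 relate to them.
4. Give the detectable readmission difference under a stated control rate. As an example, from an assumed 33% with three comparisons, 80% power needs a fall to about 10% with 64 per arm or about 12% with 80 per arm.

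The cost is wording and a less favourable stated power for readmission. No patients are added and the primary test does not change.

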13.2 Statistical Analysis Plan

13.2.1 Managing Data

PGHD, PROs and data on actionable patient care based on alert/feedback system and CRN monitoring (i.e. educated or counseled the patient, scheduled visits) will be initially stored in a secure, HIPPA-compliant cloud-based data storage system through Aetonix. We expect a total of 20 physiologic PGHD and ePRO evaluations per participant over the approximate 2 month study duration. With a total sample of 160, this yields more than 3,200 data collection encounters overall. We expect a large number of daily steps data observations per subject because functional recovery data will be continuously recorded on a daily basis over the study duration.

Data will be transferred on a daily basis from Aetonix to a REDCap (Research Electronic Data Capture) study database housed within COH and accessible only to the research team. The study biostatistician will work closely with Aetonix to coordinate real-time data transfer, auditing, and data cleaning. In the process of data transfer and mergers, the study biostatistician and Aetonix representatives will audit the data, clean the data, apply necessary formats in SAS statistical software, and export data into the REDCap database. A query system will be developed to address data validity and integrity by early identification of data collection inconsistency, data inaccuracy or incompleteness. This will be monitored by the biostatistician on a weekly basis throughout the project. Where feasible, validation rules (e.g. logic checks, format restrictions, min/max range, etc.) will be added to ensure that the data transferred and entered is valid and accurate.

In order to protect PHI data the patients will be labelled as Subject # e.g. Patient001, Patient002. Only the PI on the study and CRAs and CRN will have access to Patient Identifiers. The CRNs will have the ability to document any response to the alerts of abnormal patient generated health data as a research progress note in EPIC. The PI and the CRAs and CRNs will have access to the Aetonix app on their COH provided devices. There will be no data integration into EPIC. The devices used to transmit the patient generated health data (blood pressure, weight, temperature, pulse oximetry and heart rate) do not store any of the data and are not linked to any patient identifiers. The vivofit4 used to capture the patient steps will require that patients sign up on the Garmin website and agree to the company terms of use. These will not be linked to clinical data in any way.

13.2.1.1 *Handling Missing Sessions and Data*

Subjects with missing items among dependent variables will be compared with subjects having non-missing items to determine whether there is any bias underlying the missing data (i.e., whether data are

missing at random or can be accounted for by other variables). We will consider multiple imputation (MI) for estimating missing responses and covariates, which can be done using PROC MI in the SAS 9.4 system of software for analysis. The estimates obtained across (10 to 20) multiply imputed data sets can be combined using proc MIANALYZE, which provides valid standard errors for making inferences using the missing at random assumption.

13.2.1.2 Statistical Methods by Study Aims

We are proposing a two-group, randomized control design in which participants recruited into the study will be randomly assigned into the enhanced usual care (control) arm or the telemonitoring (intervention) arm. Both groups will be followed over the same time period which includes preoperative measurements and then up to 30 days post discharge. Data will be collected at five time points (T1: baseline, T2: pre-discharge, T3: 7-day post-discharge, T4: 14-day post-discharge, T5: 30-day post discharge). The primary outcomes for hypothesis testing are found in Aims 2, including postoperative complications, lower readmission rates, improved symptoms, QOL, and functional recovery. The primary endpoint is severity (grade) of postoperative complications from discharge to day 30 post-discharge. Descriptive statistics will be used to summarize all variables. For continuous variables, we will provide mean \pm standard deviation (SD), median, range, and sample size. For categorical variables, we will include sample size and proportion.

Specific Aim 1: Assess the feasibility, retention, and acceptability of the remote perioperative telemonitoring intervention as measured by the percentage of patients who a) agree to participate; b) complete $\geq 70\%$ of the telemonitoring; and c) report satisfaction with the intervention through structured exit interviews.

Feasibility will be assessed through: 1) the ratio of eligible participants to those enrolled and those who declines participation; 2) reasons for non-participation; 3) number of scheduled study encounters completed; 3) attrition rate between pre- and post-discharge; 4) reasons for attrition/dropout; 5) the ratio of all participants to those who completed $\geq 70\%$ of the study; These data will be descriptively reported and analyzed. Qualitative data on acceptability from exit interviews will be analyzed using the conventional content analysis approach.⁶⁵ This approach is used to describe a phenomenon where existing theory or research literature is limited. Data from the audio-recorded interviews will be transcribed and analyzed using HyperRESEARCH™ qualitative software. Transcripts will be imported allowing for the development of analytic categories, data coding, and review of coded data. All data will be read repeatedly to achieve immersion and obtain a sense of the whole. Then, data will be read word by word to derive codes. Codes will then be sorted into themes based on links and relationship. Separate investigators ([name] and [name]) will conduct a final validation review of the codes and themes to ensure consistency and clarity across all qualitative data. Data discordantly coded will be discussed for refinement and consensus purposes.

Specific Aim 2: Determine the preliminary efficacy of the remote perioperative telemonitoring intervention on surgical outcomes, healthcare utilization, PROs, and functional recovery.

Hypothesis 2.1: Patients randomized to the telemonitoring arm will experience reduced severity (grade) of postoperative complications, lower readmission rates, and improved symptoms, QOL, and daily steps.

For Specific Aim 2, the primary endpoint is the change in Comprehensive Complications index (CCI) from discharge to day 30 post-discharge. First, change in CCI will be computed. A two-sample t-test will be conducted to determine if there is significant difference between mean CCI of the intervention arm and the control arm. Trends in CCI scores will be explored over time (T2-T5). Exploratory within subjects' correlation will be examined using Pearson correlation between adjacent time points. A random-effects model will be used to study group differences in mean over time. Other variables (e.g., age and sex) may be included in the model to adjust for possible confounding.

Similar analysis will be carried out for repeatedly measured secondary endpoints (symptom severity score, QOL). Generally speaking, we expect better scores in the intervention arm than the control arm. Healthcare resource use (e.g., hospital readmission) is a secondary endpoint. At each time point, we will estimate the ER visits/readmission rates and provide confidence intervals for each arm. Further, a binomial test for comparing two proportions will be conducted to see if there is significant difference between the readmission rates of the two arms. For simplicity, Bonferroni correction will be used both in the proportions comparisons test and the confidence intervals construction.

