
The most common and successful component of cancer treatment is surgery. However, patients experience abrupt declines in functional capacity after major surgical procedures. In addition to postoperative functional decline, patients experience an increase in symptoms, such as pain, fatigue, and distress.¹⁻³ Postoperatively, these symptoms contribute to a dramatic decline in quality of life (QOL).⁴⁻⁶ Recovery from these challenges is compounded by healthcare systems-related trends, including pressures to reduce readmissions and length of stay. As a result, the majority of postoperative care and recovery takes place at home. Unfortunately, while at home physical function can decline severely before the surgical team is notified. This means that about one third of patients will become symptomatic from a complication and may require hospital readmission.^{2, 7-9}
 
A promising approach to early identification of post-discharge complications is through remote, real-time perioperative telemonitoring of patient-generated health data (PGHD) and electronic patient-reported outcomes (ePROs). In our preliminary studies, telemonitoring was feasible and acceptable in the perioperative setting.¹⁰ We found that patient-generated daily steps data was associated with the risk for postoperative complications.¹⁰ However, the current perioperative care model is largely reactive and does not address the need for monitoring and supporting postoperative recovery. Therefore, remote and scalable telemonitoring approaches are urgently needed to improve perioperative cancer care in a healthcare system that demands early discharge and reduced hospital readmissions.

Objectives:

 1. Feasibility Retention and acceptability of the intervention through statistics of participation, intervention, completion (retention) rates and qualitative data from exit interviews. 2. Surgical outcomes (post operative complications), healthcare utilization (postoperative complications, readmissions), PROs (symptoms, QOL) and functional recovery (pedometer) will be examined by treatment arm

Study Design:
Pilot RCT (1:1 randomization)
Endpoints:
Primary: severity (grade) of postoperative complications from discharge to day 30 post discharge.
Sample Size:
160 patients (80 per arm)
Estimated Duration of the Study
30 months
Summary of Subject Eligibility Criteria:
Study eligibility criteria include:

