2.2 Overview of Proposed Study

This is a pilot RCT (1:1 randomization) of a remote perioperative telemonitoring intervention in major abdominal cancer surgery. We will focus on GI malignancies, because the surgical procedures, extent of resection, and expected surgical outcomes are similar. In Aim 1, we will assess the feasibility, retention, and acceptability of the intervention through statistics of participation, intervention completion (retention) rates, and qualitative data from exit interviews. In Aim 2, surgical outcomes (post-operative complications), healthcare utilization (postoperative complications, hospital readmissions), PROs (symptoms, QOL), and functional recovery (pedometer steps) will be examined by treatment arm. Our primary endpoint is severity (grade) of postoperative complications from discharge to day 30 post-discharge. This study will be conducted in compliance with the protocol, Good Clinical Practice (GCP) and the applicable regulatory requirements.

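### The primary endpoint is defined in two ways, as severity of post-discharge complications and as change in CCI, and no scoring rule makes them the same variable

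*Combined protocol and SAP*

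**What the plan says.** Three places in the combined protocol and SAP agree. The synopsis, under Endpoints, gives "Primary: severity (grade) of postoperative complications from discharge to day 30 post discharge". Section 2.2 says "Our primary endpoint is severity (grade) of postoperative complications from discharge to day 30 post-discharge". The opening of section 13.2.1.2 says "The primary endpoint is severity (grade) of postoperative complications from discharge to day 30 post-discharge". Hypothesis 2.1, restated in that section, is also about severity: "Patients randomized to the telemonitoring arm will experience reduced severity (grade) of postoperative complications".

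The Aim 2 analysis text in section 13.2.1.2 differs: "For Specific Aim 2, the primary endpoint is the change in Comprehensive Complications index (CCI) from discharge to day 30 post-discharge". It continues "First, change in CCI will be computed", and then "A two-sample t-test will be conducted to determine if there is significant difference between mean CCI of the intervention arm and the control arm". That last sentence mentions neither change nor a time point.

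Other relevant text:

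- Sections 10.0 and 11.1 (Table 1) name the CCI as the measure of complications, assessed pre-discharge and at days 2, 7, 14 and 30.
- Section 12.1.3 describes the CCI as running from 0 to 100, built on Clavien-Dindo grades and covering the whole postoperative course.
- Section 1.0 starts telemonitoring before surgery and continues it in hospital. Section 5.1 places randomisation after the preoperative baseline assessment.
- Section 13.1.1 powers the trial for a standardised effect of 0.5, without naming a CCI variable, a standard deviation or a raw difference.

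**The concern.** Severity of complications over a period and change in a score between two dates are different quantities unless the scoring rule makes them equal. Nothing says whether the CCI at each visit accumulates from surgery or covers only the interval since discharge or the last visit.

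If it is cumulative, the change approximates the burden added after discharge. On an index bounded at 100, that increment need not equal the severity of the post-discharge events. If it is interval-based, the change subtracts in-hospital severity, so a patient with a severe in-hospital complication and a milder one at home appears to improve.

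The discharge CCI is also not a baseline. It is measured after randomisation and after telemonitoring has begun, so subtracting it can remove or distort part of a treatment effect.

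Two uses of the result depend on this. Section 13.1.1 claims adequate power for the primary endpoint. Section 1.0 says the pilot will supply the effect size for sizing a Phase III trial. An effect size is usable only if the variable it describes is known.

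**Working it through.** **The plan's own figure.** For d = 0.5, two-sided alpha 0.05, 80% power and a two-sample t-test, the exact solution is 63.77, rounded up to 64 per arm (128 in total), with 80.1% power. Allowing for 20% attrition, 128 / 0.8 = 160. Section 13.1.1 reproduces. The calculation uses only the standardised effect, so it does not show which CCI variable is meant.

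**Definitions.** Let D be the CCI at discharge and P the CCI from post-discharge complications alone. The change from discharge to day 30 is then:

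- cumulative, additive: min(D + P, 100) − D
- cumulative, root-sum-of-squares: √(D² + P²) − D
- cumulative, worst complication only: max(D, P) − D
- interval: P − D

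The documents give no rule for combining complications, so these are assumed readings that span a range.

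**One patient.** Take P = 30. If D = 0, the change is 30 under all four rules. If D = 30, it is 30 (additive), √1800 − 30 = 12.4 (root-sum-of-squares), 0 (worst only) or 0 (interval). P itself is 30 in every case.

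**Between arms.** Inputs:

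- From the plan: 64 per arm, a two-sided 0.05 t-test, d = 0.5 and about one third of patients with a complication at home (synopsis and section 1.0).
- Assumed: d = 0.5 applies to P; each complication scores uniformly from 10 to 50; 20%, 40% or 60% of both arms have an in-hospital complication; post-discharge risk is either independent of D or doubled when D > 0.

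A severity that is uniform on 10-50 has mean 30 and mean square 30² + 40²/12 = 1033.3. With one third of controls affected, mean P is 10 and its variance is 344.4 − 100 = 244.4. With 11.3% affected on telemonitoring, mean P is 3.39 and its variance is 116.8 − 11.5 = 105.3. The average variance is 174.9 (SD 13.2), so d = 6.61 / 13.2 = 0.50, as required.

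Power from 20,000 simulated trials per setting:

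| Variable tested | 20% indep. | 20% doubled | 40% indep. | 40% doubled | 60% indep. | 60% doubled |
|---|---|---|---|---|---|---|
| P (post-discharge CCI) | 81% | 81% | 81% | 81% | 81% | 81% |
| Change, additive | 81% | 81% | 81% | 81% | 81% | 81% |
| Change, root-sum-of-squares | 78% | 76% | 75% | 72% | 72% | 70% |
| Change, worst only | 73% | 68% | 65% | 56% | 55% | 47% |
| Change, interval | 52% | 59% | 43% | 49% | 40% | 44% |

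A hand check of the interval row, independent case: the variance of D is 0.2 × 1033.3 − 6² = 170.7 at 20%, and 620 − 18² = 296 at 60%. So d = 6.61 / √345.6 = 0.36 and 6.61 / √470.9 = 0.30, consistent with 52% and 40%. With a skewed severity distribution, 100 × Beta(1.5, 4), the ranges are 82-83% for P, 71-79% for root-sum-of-squares, 56-77% for worst only and 36-57% for interval.

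**Subtraction is not neutral.** Suppose telemonitoring only lowered in-hospital complications from 40% to 20%, with one third of both arms affected after discharge. P then does not differ between arms. The change looks worse with telemonitoring by 0 (additive), 1.1 (root-sum-of-squares), 1.5 (worst only) or 30 × (0.40 − 0.20) = 6.0 points (interval).

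**If mean CCI means the day-30 score.** Assume 0.5 SD on the day-30 CCI, equal SDs at discharge and day 30, correlation ρ, and no arm difference at discharge. The effect on change is 0.5 / √(2(1 − ρ)). With 64 per arm, power for the change is 51% at ρ = 0, 66% at 0.3, 80% at 0.5, 95% at 0.7 and 99% at 0.8. The two analyses agree only at ρ = 0.5. If ρ = 0.5 and 25% or 50% of the effect is already present at discharge, power for the change is 56% or 29%.

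**The case against.** The strongest reply is that this is one endpoint loosely worded. The CCI is the only complication measure in sections 10.0 and 11.1, and section 12.1.3 describes it as covering the whole postoperative course, which suggests cumulative scoring. Change from discharge to day 30 is then a natural way to capture complications arising in that window, and mean CCI in the t-test sentence probably means mean change. How the index combines complications is set in the publications the plan cites. The interval and worst-only readings, which give the largest losses, fit section 12.1.3 poorly; without them power is 70-81%. The 0.5 was fixed on P here; had it been meant for the change, the change would have about 80% power. The in-hospital scenario is invented, and with 64 per arm the root-sum-of-squares change would reject in only about 7% of trials in that case.

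Most of this is fair as to size. Cumulative scoring is the likelier reading, and the larger losses should carry less weight. It does not remove the conflict. Even under cumulative scoring, change equals post-discharge severity only if scores add. Declaring the CCI cumulative and testing the change would settle the wording, but would leave a variable that can differ from the endpoint stated three times. That 0.5 could belong to either variable is itself part of the problem.

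It is also true that a window starting at discharge conditions on a post-randomisation event. The endpoint as stated already does so, which is why a supplementary analysis from surgery onward is suggested.

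**Conclusion.** The concern holds. Current text gives two primary endpoint definitions, and the t-test sentence does not settle which variable is compared. The size depends on a rule the plan does not state. Under the assumptions shown, testing the change rather than post-discharge CCI costs nothing with additive scoring, about 3 to 11 percentage points of power with root-sum-of-squares (70-78% against 81%), and more under the less likely worst-only (47-73%) and interval (40-59%) readings. These figures rest on assumed complication rates and severities and on placing d = 0.5 on post-discharge CCI. The conflict in the text does not depend on them. It should be fixed before analysis, so that the primary variable is not chosen after the data are seen and the effect size carried to Phase III belongs to a known quantity.

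**What to change.** Use one primary variable in the synopsis, section 2.2 and both parts of section 13.2.1.2: CCI scored from complications with onset between discharge and day 30 post-discharge, set to 0 for a patient discharged alive with none. Compare it between arms with the planned two-sample t-test, without subtracting the discharge CCI. Replace the references to change in CCI and the undated mean CCI with this variable, and tie the 0.5 effect size in section 13.1.1 to it.

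State whether the visit CCI scores used for trends are cumulative or interval. Name those visits by day: T5 is day 30 in section 13.2.1.2 but day 14 in sections 10.0 and 11.1, so a T2 to T5 range is ambiguous.

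Optionally, add a sensitivity analysis of CCI from surgery to day 30 post-discharge. This also captures in-hospital effects and patients who die before discharge.

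The cost is wording, since the CCI is already assessed pre-discharge and at days 2, 7, 14 and 30. The one practical addition is that each complication must be dated relative to discharge. Section 11.1 lists postoperative events and discharge date among the data collected, but not onset dates.
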